2.0 TRIAL DESIGN

2.1 Trial Design

This will be an open label, single center, single arm, pilot trial based on the established dose from the phase 1 trial.

[figure not shown]
Pembrolizumab 200 mg will be administered as a single agent intravenous infusion every 3 weeks (one cycle=21 days) for up to 24 cycles.

Disease evaluation will be done at baseline and at each cycle. Patients will continue with therapy until they have progressive disease or intolerable side effects for 8 cycles initially, with an option to continue therapy beyond 8 cycles if there is continued clinical benefit without serious adverse events.

In patients who show a continued response (\geq minor response) after 8 cycles, treatment can be continued for an additional 16 cycles to a maximum of 24 cycles.

In patients who show a continued response (\geq minor response) after 8 cycles, but who choose to stop treatment after 8 cycles of therapy and then experience progressive disease within 6 months of treatment stop, treatment can be restarted for an additional 16 cycles to a maximum of 24 cycles.

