6.2 Response Criteria

Response assessments will be performed on Day 1 of each cycle during Cycle 1-24 and at the end of Cycle 24.

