6.2.1 Light chain only disease

- a) If patient does not have presence of "measurable" serum or urine M-protein (those are negative in electrophoresis), but has either a serum kappa or lambda FREE light chain of 10 mg/dL along with an abnormal kappa to lambda free light chain ratio, patient is considered to have "measurable" disease.
- b) The serum free light chain (FLC) assay is of particular use in monitoring response to therapy in patients who have oligo-secretory disease. When using this assay, it is important to note that the FLC levels vary considerably with changes in renal function and do not solely represent monoclonal elevations. Thus both the level of the involved and the uninvolved FLC isotype (i.e., the involved/uninvolved ratio or involved-uninvolved difference) should be considered in assessing response. The serum FLC assay should be used in assessing response only if the baseline serum and/or urine M proteins are not "measurable" by traditional criteria, and the baseline level of the involved FLC is 10mg/dL and clonal (abnormal ratio). Patients included on the study on the basis of FLC alone (i.e., no measurable serum/urine) should be the only ones who are evaluated using FLC response criteria. The others should follow usual criteria and ignore FLC results.
- c) In order to be classified as a hematologic response, confirmation of serum monoclonal protein, serum immunoglobulin free light chain (when primary determinant of response) and urine monoclonal protein (when primary determinant of

response) results must be made by verification on two consecutive determinations.

- d) Caution must be exercised to avoid rating progression or relapse on the basis of variation of radiological technique alone. Compression fracture does not exclude continued response and may not indicate progression. When progression is based on skeletal disease alone, it should be discussed with the PI before removing the patient from the study.

6.2.2 Evaluation of response Criteria by modified International Myeloma Working Group Criteria for Multiple Myeloma

a) Stringent Complete Response (sCR)

- Complete Response as defined below plus: Normal FLC ratio and absence of clonal cells in bone marrow by immunohistochemistry or immunofluorescence (presence/ absence of clonal cells is based on the kappa/ lambda ratio).

b) Complete Response (CR)

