6.2.6 Overall response rates after 8 and 24 cycles of treatment

Overall response rates (ORR) is PR+VGPR+CR+sCR.

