8.2.5 Sponsor Responsibility for Reporting Adverse Events

All Adverse Events will be reported to regulatory authorities, IRB and investigators in accordance with all applicable global laws and regulations.

First stage: The principal investigator will submit a response/toxicity summary to the IND Medical monitor after the first 12 subjects have completed 8 cycles

Second Stage: The principal investigator will submit a response/toxicity summary to the IND Medical monitor after additional 4 subjects have completed 8 cycles

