9.0 STATISTICAL ANALYSIS PLAN

The overall response (\geq partial response) after 8 cycles of treatment is the primary endpoint. The trial will be conducted by the Simon's Minimax design and the response rate will be estimated accordingly (Simon, 1989).

It is assumed that Pembrolizumab will have a target response rate after 8 cycles of treatment of 25%. A response rate of 5% or lower is considered a failure and the new regimen will be rejected under this circumstance. When the probability of accepting a "bad" regimen (i.e. response rate $\leq 5\%$) is 0.05 and the probability of rejecting a "good" regimen (i.e. response rate $\geq 25\%$) is 0.20, Simon's Minimax design requires to enter 12 patients in the first stage. If no patient responds to the treatment, the trial will be stopped and the regimen will be declared as ineffective. If there is at least one response observed, 4 more patients will be entered in the study to reach a total of 16 patients. By the end of the study, the new regimen will be rejected if response rate is less than or equal to 2/16 and will be accepted otherwise. The operating characteristics of the trial are given as follows. When the true response rate is 5% the probability of stopping the trial early is 54%. On the other hand, if the true response rate is 0.25, the probability to stop the trial early is 3.2%. The expected sample sizes are 13.8 and 15.9 when the true response rates are 0.05 and 0.25, respectively.

If the number of responses required for moving the trial to the second stage has not been achieved, the patient enrollment will be halted until enough responses observed.

Summary statistics will be provided for continuous variables. Frequency tables will be used to summarize categorical variables. The response rate and its 95% confidence interval will be calculated. The distribution of time-to-event endpoints including progression free survival and overall survival will be estimated using the method of Kaplan and Meier.

Toxicity data will be summarized by frequency tables for all patients. For the efficacy endpoints, intent-to-treat analysis will be applied to the eligible patients. For the toxicity endpoint, per-treated analysis will be performed to include any patient who received the treatment regardless of the eligibility nor the duration or dose of the treatment received.

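### Does the enrolment-halt sentence in Section 9.0 undo the stop at 0 responses in 12 patients?

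*Combined protocol and SAP*

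**What the plan says.** Section 9.0 opens by stating that overall response (partial response or better) "after 8 cycles of treatment is the primary endpoint". It then sets out a Simon minimax design with an unacceptable rate of 5%, a target rate of 25%, 12 patients in stage 1 and 16 in total, and rejection of the regimen at 2/16 or fewer. The stage 1 rule is explicit: "If no patient responds to the treatment, the trial will be stopped and the regimen will be declared as ineffective". One response is enough to open stage 2.

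The next paragraph is one sentence. If the number of responses needed for stage 2 has not been achieved, "the patient enrollment will be halted until enough responses observed". It names no assessment point and does not refer back to the stop rule.

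Other sections bear on the timing. Section 8.2.5 has the investigator send a first-stage response and toxicity summary "after the first 12 subjects have completed 8 cycles". Under Section 2.1, patients with at least a minor response after Cycle 8 may go on: "treatment can be continued for an additional 16 cycles to a maximum of 24 cycles". Section 6.2 adds: "Response assessments will be performed on Day 1 of each cycle during Cycle 1-24 and at the end of Cycle 24". The heading of Section 6.2.6 reads "Overall response rates after 8 and 24 cycles of treatment". For a response to count, Section 6.2.1 says the protein and light-chain "results must be made by verification on two consecutive determinations".

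**The concern.** With a stage 1 limit of zero, too few responses for stage 2 and no response in 12 are the same state. One sentence ends the trial in that state; the other suspends enrolment, and the only ending it names is a response. A patient with a minor response at Cycle 8 may stay on treatment and be assessed every cycle to Cycle 24, so a first partial response after Cycle 8 is possible. Taken literally, it could reopen a trial that stood at 0/12 on the primary endpoint.

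The stop at 0/12 is what produces the stated early-stopping probability and expected sample size. It is also the only efficacy-based stopping rule; Section 5.12 lists only safety and drug-development grounds. If 0/12 were not final, the stated operating characteristics would not describe the rule in use, and a few more asymptomatic patients might receive an inactive drug.

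**Working it through.** **Inputs.** From Section 9.0: p0 = 0.05, p1 = 0.25, n1 = 12, stop at 0, n = 16, accept at 3 or more. Stated figures: early stopping (PET) 54% and 3.2%; expected N 13.8 and 15.9. From Section 1.0: enrolment over 6 months to one year, and 18 months for the 8-cycle response data. From Section 2.1: 21-day cycles, at most 24.

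**1. The plan's own figures, with 0/12 final.** PET = (1 − p)^12 and E[N] = 16 − 4 × PET.

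- p = 0.05: PET = 0.95^12 = 0.5404; E[N] = 16 − 4(0.5404) = 13.84.
- p = 0.25: PET = 0.75^12 = 0.0317; E[N] = 16 − 4(0.0317) = 15.87.
- Acceptance = P(at least 1 in the first 12 and at least 3 in 16) = 0.0427 at p = 0.05 (type I error) and 0.8013 at p = 0.25 (power).

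All four stated figures reproduce. An exhaustive search at these error rates also returns 0/12 and 2/16 as the minimax design.

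**2. Which reading fits the text.**

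- The stop rule covers 0/12 and ends the trial. A stopped trial has no enrolment left to halt, so the open-ended reading would cancel an explicit rule.
- As a pause, the sentence has a job. The endpoint takes 8 × 21 = 168 days (about 5.5 months) per patient, and the plan must say whether patient 13 may enter before the first 12 have been evaluated. The answer is no, unless the one response needed has already been seen. If all 12 are evaluated with none, the stop rule applies.
- The response in question is the one after 8 cycles, both as the primary endpoint and as the target rate. Section 8.2.5 places the first-stage summary at the same point.
- The timeline agrees. Twelve months of enrolment plus 5.5 months is 17.5, close to the planned 18. A halt that ran to Cycle 24 would take 24 × 21 = 504 days (about 16.6 months), and stage 2 would need another 5.5. That is 22.1 months before any time for enrolment.

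**3. Size if the sentence were nevertheless applied literally.** The documents give no rate of first partial response after Cycle 8. Let q be an assumed chance per patient. At p = 0.05, PET = 0.5404 × (1 − q)^12. If late responses only reopen enrolment, a reopened trial needs at least 3 responses in the 4 new patients, with probability 0.00048. Type I error is then 0.0427 + 0.5404 × [1 − (1 − q)^12] × 0.00048.

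| Assumed q | PET | E[N] | Type I error, only 8-cycle responses counted |
|---|---|---|---|
| 0 | 0.540 | 13.84 | 0.0427 |
| 1% | 0.479 | 14.08 | 0.0427 |
| 2% | 0.424 | 14.30 | 0.0427 |
| 5% | 0.292 | 14.83 | 0.0428 |
| 10% | 0.153 | 15.39 | 0.0429 |
| always reopens | 0 | 16 | 0.0429 |

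The largest rise in expected N is 16 − 13.84 = 2.16 patients. Power in the last row is 0.8029 against 0.8013.

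**4. If late responses also counted toward 3/16.** Suppose one late response is credited, and only in reopened trials. With f the share of 0/12 trials that reopen, type I error is 0.0427 + f × 0.5404 × P(at least 2 of 4) = 0.0427 + f × 0.5404 × 0.01402. That is 0.0434, 0.0446 and 0.0503 for f = 10%, 25% and 100%. If late responses counted for every patient, the response rate would become 0.05 + 0.95q, and acceptance at a true 8-cycle rate of 5% would be 0.0655, 0.0932, 0.199 and 0.414 for q = 1%, 2%, 5% and 10%. Those last figures describe a different endpoint from the one in Section 9.0.

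**The case for a change.** The best case for a change is that the halt sentence carries no limit, that Section 8.2.5 is a reporting duty with no decision rule attached, and that in an open-label trial the choice between readings would be made with the data in view. A single patient decides the stage 1 outcome. One replacement sentence would settle the matter at almost no cost.

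There is also a gap at the boundary. A partial response first met at the end of Cycle 8 is confirmed only at a later determination, and Section 9.0 does not say how that patient counts when the stage 1 decision is made.

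What stands is that the wording is loose and the confirmation step is not spelled out. Neither leaves the decision open. Finality at 0/12 comes from the stop rule itself, so it does not depend on Section 8.2.5. For confirmation, the sensible course is to await the second determination before declaring 0/12. Section 6.2.1 fixes no interval between determinations, and Section 5.6.1.4 allows extra laboratory tests if clinically indicated. Assessments to Cycle 24 and the 24-cycle response rate describe longer follow-up; nothing in Sections 6.2 or 6.2.6 feeds them into the stage 1 count. Reopening would in practice also need a patient with a minor but not a partial response at Cycle 8 who improves later, so the always-reopens row is a bound and not a forecast.

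**Conclusion.** No change follows. The sentence is a loosely worded accrual pause, and the explicit stop at 0/12 governs once the first 12 patients have been evaluated on the 8-cycle endpoint. On that reading every figure in Section 9.0 is right: PET 54% and 3.2%, expected N 13.8 and 15.9, with exact type I error 4.27% and power 80.1%. Tighter wording would write down what the plan already implies and would alter no number or conclusion.

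The literal reading costs at most 2.2 patients in expected sample size at a true rate of 5%. The maximum stays at 16 and type I error stays at or below 4.29%. This rests on the final 3/16 decision counting only 8-cycle responses, as the primary endpoint requires. The intermediate PET and expected-N values rest on assumed late-response rates that the documents do not give. Larger error rates arise only if late responses are counted toward the primary endpoint, which the plan does not provide for.

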3.0 OBJECTIVES & HYPOTHESES

3.1 Primary Objective & Hypothesis

(1) **Objective:** ORR (partial response [PR] or better) after 8 cycles of treatment per IMWG criteria for multiple myeloma (MM)¹

Hypothesis: In this pilot, exploratory trial, we hypothesize that pembrolizumab in intermediate and high-risk smoldering multiple myeloma (SMM) will have a target response rate after 8 cycles of treatment of at least 25%. A response rate of 5% or lower will be considered a failure and this new regimen will be rejected.

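### Does a 95% confidence interval beside a one-sided 5% Simon rule leave the trial's accept-or-reject decision contradicted by its own interval?

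*Combined protocol and SAP*

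**What the plan says.** Section 3.1 (Primary Objective & Hypothesis) sets the failure line: "A response rate of 5% or lower will be considered a failure and this new regimen will be rejected". Section 9.0 repeats it and turns it into a two-stage rule with a target of 25%, a 0.05 chance of accepting a bad regimen and a 0.20 chance of rejecting a good one.

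- **Stage 1:** 12 patients. "If no patient responds to the treatment, the trial will be stopped and the regimen will be declared as ineffective".
- **Stage 2:** with at least one response, four more patients enter, for 16 in all. The regimen is rejected at 2/16 or fewer and accepted otherwise.

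On estimation, Section 9.0 says of the Simon design that "the response rate will be estimated accordingly". Later, in the paragraph on summary statistics and frequency tables, it says "The response rate and its 95% confidence interval will be calculated". It names no interval method and no adjustment for the two stages, and it gives the interval no part in the decision.

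**The concern.** The Simon rule is one-sided: its 0.05 is an upper-tail error at a true rate of 5%. A two-sided 95% interval spends only 0.025 in that tail, so the interval sets a stricter standard than the rule. A result that just passes the rule can carry an interval that still contains 5%, the rate the protocol calls failure. A reader could then ask whether the regimen has been shown to beat 5% at all.

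Two further points add to the worry. At 0/12, where the regimen is declared ineffective, an exact 95% interval still reaches the 25% target. And because no method is named, the simple normal-approximation (Wald) interval is not ruled out, although it has zero width at 0/12. At stake would be a pilot whose two outputs, a decision and an estimate from 16 patients, appear to disagree.

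**Working it through.** **Inputs (Section 9.0).** p0 = 0.05, p1 = 0.25, error rates 0.05 and 0.20; stop at 0/12; reject at 2/16 or fewer; accept at 3/16 or more; 95% interval.

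**1. Reproduce the design.** With X1 the responses among the first 12 patients and X2 those among the next 4:

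- P(stop) = (1 − p)^12, which is 0.95^12 = 0.540 and 0.75^12 = 0.032.
- Expected sample size = 12 + 4 × (1 − P(stop)), which is 13.84 and 15.87.
- P(accept) = P(X1 = 1)·P(X2 ≥ 2) + P(X1 = 2)·P(X2 ≥ 1) + P(X1 ≥ 3).
 - At 5%: 0.0048 + 0.0183 + 0.0196 = 0.0427.
 - At 25%: 0.0332 + 0.1588 + 0.6093 = 0.801.

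These match the plan's 54%, 3.2%, 13.8 and 15.9, and both error rates are met.

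**2. Exact (Clopper-Pearson) intervals.** For x responses in n, the lower limit solves P(X ≥ x | p) = a and the upper limit solves P(X ≤ x | p) = a, with a = 0.025 for 95% and 0.05 for 90%.

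| Result | Decision | Exact 95% | Exact 90% |
|---|---|---|---|
| 0/12 | stop | 0–26.5% | 0–22.1% |
| 1/16 | reject | 0.2–30.2% | 0.3–26.4% |
| 2/16 | reject | 1.6–38.3% | 2.3–34.4% |
| 3/16 | accept | 4.0–45.6% | 5.3–41.7% |
| 4/16 | accept | 7.3–52.4% | 9.0–48.4% |

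**3. Accept side.** The 95% interval at 3/16 contains 5% because the attained tail, 0.0427, exceeds 0.025. Inverting the two-stage acceptance probability instead gives a lower limit of 4.06%, so allowing for the interim look makes no difference. At 4/16 the conflict is gone.

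The conflict also depends on the method. Other 95% lower limits at 3/16 are Wilson 6.6%, Agresti-Coull 5.8%, Jeffreys 5.6%, mid-p 5.002%, and Wald below zero (0.1875 − 1.96 × √(0.1875 × 0.8125/16) = −0.004).

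**4. Stop and reject side.** The interval at 0/12 contains 5%, which agrees with not accepting the regimen. It also reaches 25% because P(0/12 | 25%) = 0.032 exceeds 0.025. Stopping there is a futility decision paid for out of the 0.20 error rate, so it says nothing about a mismatch with the one-sided 0.05. If containing 25% did contradict a rejection, then 1/16 and 2/16 would be contradicted too, and the 90% column shows they still would be at that level.

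**5. How often, and is the interval valid?** Exact two-stage probabilities:

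| True rate | P(3/16) | P(accept) | Share of acceptances at 3/16 |
|---|---|---|---|
| 5% | 3.6% | 4.3% | 84% |
| 25% | 20.6% | 80.1% | 26% |

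Summing over all two-stage outcomes, the exact 95% interval covers the true rate with probability 97.6% to 99.3% at true rates of 5, 10, 15, 20 and 25%. Wald coverage is 46% at 5% and 90% at 25%.

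**The case for a change.** The best case for a change is that 3/16 is no rare corner. If the drug works at the target rate, about one trial in five ends there, and with an exact interval the report would pair acceptance with a range that includes the failure rate. With the method left open, an analyst who sees 3/16 could choose Wilson to support the decision or the exact method to undercut it, and nothing in the text forbids Wald. One sentence written beforehand would settle this at no cost in patients or data.

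The arithmetic stands, and so does the observation that the method is unnamed. The consequence does not. Whichever interval is chosen, 3/16 is an acceptance, because Section 9.0 fixes the verdict on the count. An interval at a stricter level than the test answers a different question and does not reopen the verdict. The Wald figures describe a method the plan never mentions and that few statisticians would pick for 0/12 or 3/16. Moving to 90% would align the interval with the rule at 3/16, but it would give readers a narrower range from 16 patients and would still contain 25% at 1/16 and 2/16. Experienced statisticians differ on that choice.

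**Conclusion.** The concern does not call for a change. What holds is narrow: with an exact method, the single result 3/16 would be accepted with a 95% interval of 4.0% to 45.6%, which includes 5%. The claim about 0/12 does not hold, since 0% to 26.5% is compatible with the 5% failure rate and the stop is governed by the other error rate.

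The decision rule reproduces (attained error 0.0427, power 0.801), rests on counts and is untouched by the interval. The planned 95% level gives a valid, somewhat conservative interval when computed exactly. The unnamed method is a gap that a competent analyst fills with a standard small-sample method and states in the report, and the level is a fair trade-off between matching the test and following the usual reporting convention.

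This rests on two assumptions: that the analyst does not use Wald, and that the interval is read as description of a pilot result, which is where Section 9.0 places it. A report that ended at 3/16 would do well to say that the lower limit falls below 5% because the interval is stricter than the one-sided rule. That is a matter for the write-up.

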10.0 LABELING, PACKAGING, STORAGE AND RETURN OF CLINICAL SUPPLIES

10.1 Investigational Product

The investigator shall take responsibility for and shall take all steps to maintain appropriate records and ensure appropriate supply, storage, handling, distribution and usage of investigational product in accordance with the protocol and any applicable laws and regulations.

Clinical Supplies will be provided by Merck as summarized in Table 6.

Table 6 Product Descriptions

Product Name & Potency	Dosage Form
Pembrolizumab 50 mg	Lyophilized Powder for Injection
Pembrolizumab 100 mg/ 4mL	Solution for Injection

10.2 Packaging and Labeling Information

Clinical supplies will be affixed with a clinical label in accordance with regulatory requirements.

10.3 Clinical Supplies Disclosure

This trial is open-label; therefore, the subject, the trial site personnel, the Sponsor and/or designee are not blinded to treatment. Drug identity (name, strength) is included in the label text; random code/disclosure envelopes or lists are not provided.

10.4 Storage and Handling Requirements

Clinical supplies must be stored in a secure, limited-access location under the storage conditions specified on the label.

Receipt and dispensing of trial medication must be recorded by an authorized person at the trial site.

Clinical supplies may not be used for any purpose other than that stated in the protocol.

10.5 Returns and Reconciliation

The investigator is responsible for keeping accurate records of the clinical supplies received from Merck or designee, the amount dispensed to and returned by the subjects and the amount remaining at the conclusion of the trial.

Upon completion or termination of the study, all unused and/or partially used investigational product will be destroyed at the site per institutional policy. It is the Investigator's responsibility to arrange for disposal of all empty containers, provided that procedures for proper disposal have been established according to applicable federal, state, local and institutional guidelines and procedures, and provided that appropriate records of disposal are kept.

